5.4 Treatment blinding

Patients, investigator staff, persons performing the assessments, and data analysts will remain blind to the identity of the treatment from the time of randomization until database lock, using

the following methods: (1) Randomization data are kept strictly confidential until the time of unblinding, and will not be accessible by anyone else involved in the study with the following exceptions: Drug Supply Management, PK analyst and the IRT staff. (2) The identity of the treatments will be concealed by the use of study drug that are all identical in packaging, labeling, schedule of administration, and appearance.

The randomization codes associated with patients from whom PK samples are taken will be disclosed to PK analysts who will keep PK results confidential until database lock.

Unblinding will only occur in the case of patient emergencies (see [Section 5.5.9](#)) and at the conclusion of the study. The external DMC and independent Contract Research Organization (CRO) will have access to unblinded data, as further described in [Section 8.4](#).

5.5 Treating the patient

Sponsor qualified medical personnel will be readily available to advise on trial related medical questions or problems.

5.5.1 Patient numbering

Each patient is uniquely identified by a Subject Number which is composed of the site number and a sequential number. Once assigned to a patient, the Subject Number will not be reused.

Upon signing the informed consent form, the patient is assigned the next sequential number. The investigator or his/her staff will contact the IRT and provide the requested identifying information for the patient to register them into the IRT. The site must select the Case Report Form (CRF) book with a matching Subject Number from the Electronic Data Capture (EDC) system to enter data.

If the patient fails to be randomized for any reason, the IRT must be notified within 2 days that the patient was not treated. The reason for not being treated will be entered on the Screening Disposition CRF.

A patient may fail the Screening epoch one time; Investigators may re-screen a patient if there is reasonable certainty that reasons for screen failure will be resolved prior to or during a repeat screening attempt. Some examples of re-screening reasons are listed below. If needed, questions regarding re-screen eligibility may be discussed with Novartis. Should this occur, the site should re-consent the patient and assign a new subject identification number. Once randomized, the subject identification number must remain constant throughout the entire clinical study.

- Laboratory value(s) out of range due to sampling error or that might be within range after medically-appropriate supplementation. (Note: Before screen failing and then re-screening the subject, efforts should be made to repeat the laboratory assessment(s) during the original initial screening phase.)
- The patient has a medical condition that can be stabilized or resolved prior to the repeat screening attempt.

Patients may NOT be re-screened if the reason for screen failure was due to not meeting the requirements of the proprietary screening algorithm based on assessment of their 24-hour average pain intensity scores recorded in the eDiary device.

5.5.2 Dispensing the study drug

Each study site will be supplied with study drug in packaging of identical appearance.

The study drug packaging has a 2-part label. A unique medication number is printed on each part of this label which corresponds to one of the treatment arms and a specific dose. Investigator staff will identify the study drug package(s) to dispense to the patient by contacting the IRT and obtaining the medication number(s). Immediately before dispensing the package to the patient, investigator staff will detach the outer part of the label from the packaging and affix it to the source document (Drug Label Form) for that patient's unique subject number.

5.5.3 Handling of study and additional treatment

5.5.3.1 Handling of study treatment

Study treatment must be received by a designated person at the study site, handled and stored safely and properly, and kept in a secured location to which only the investigator and designees have access. Upon receipt, all study treatment must be stored according to the instructions specified on the labels. Clinical supplies are to be dispensed only in accordance with the protocol. Technical complaints are to be reported to the respective Novartis Country Pharma Organization (CPO) Quality Assurance.

Medication labels will be in the local language and comply with the legal requirements of each country. They will include storage conditions for the study treatment but no information about the patient except for the medication number.

The investigator must maintain an accurate record of the shipment and dispensing of study treatment in a drug accountability log. Monitoring of drug accountability will be performed by monitors during site visits or remotely and at the completion of the trial. Patients will be asked to return all unused study treatment and packaging at every study visit and at the end of the study or at the time of discontinuation of study treatment.

At the conclusion of the study, and as appropriate during the course of the study, the investigator will return all unused study treatment, packaging, drug labels, and a copy of the completed drug accountability log to the Novartis monitor or to the Novartis address provided in the investigator folder at each site.

5.5.3.2 Handling of additional treatment

Not applicable.

5.5.4 Instructions for prescribing and taking study treatment

For all treatment groups, each dose will be self-administered orally as two capsules with a full glass of non-carbonated water twice daily, consisting of a morning dose and an evening dose. The study medication should be taken on an empty stomach at least one hour before a meal or

at least two hours after a meal. **At the scheduled study visits where PK is collected (refer to Table 6-1), patients should be instructed not to take their morning dose of study medication (and duloxetine if applicable) prior to arriving at the site and completing the necessary assessments.** Patients should bring their duloxetine (if applicable) with them to the study visits where PK is collected so it may be administered after the PK assessment, as required.

All kits of study treatment assigned by the IRT will be recorded/databased in the IRT.

The investigator must promote compliance by instructing the patient to take the study treatment exactly as prescribed and by stating that compliance is necessary for the patient's safety and the validity of the study. The patient must also be instructed to contact the investigator if he/she is unable for any reason to take the study treatment as prescribed.

5.5.5 Permitted dose adjustments and interruptions of study treatment

Investigational or other treatment dose adjustments and/or interruptions are not permitted.

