5.6.2 Discontinuation of study treatment

Discontinuation of study treatment for a patient occurs when study drug is stopped earlier than the protocol planned duration, and can be initiated by either the patient or the investigator.

The investigator must discontinue study treatment for a given patient if, on balance, he/she believes that continuation would negatively impact the risk/benefit of trial participation.

Study treatment must be discontinued under the following circumstances:

- Patient wish
- Pregnancy (see [Section 6.5.6](#) and [Section 7.6](#))
- Use of prohibited treatment that requires study treatment discontinuation as described in [Table 5-2](#)
- Positive urine drug screen
- Any situation in which study participation might result in a safety risk to the patient
- Unsatisfactory therapeutic effect
- Patient's condition no longer requiring study treatment
- Any laboratory abnormalities that in the judgment of the investigator, taking into consideration the patient's overall status, prevents the patient from continuing participation in the study

In addition, study treatment must be interrupted/ discontinued under the following circumstances:

- Emergence of the following adverse events:
 - Skin rash – In the event a skin rash occurs while on study medication, initial evaluation by a qualified clinician is required. Identified common dermatologic conditions (i.e. insect bites, poison ivy etc.) can be evaluated and treated per standard of care by investigator. In cases of suspected allergic dermatitis does not respond to treatment, consultancy with an independent dermatologist for follow-up is required

with appropriate documentation in patient's source. Study treatment should be interrupted if allergic dermatitis is suspected. The following assessments should be done at the time of determination and recorded in the appropriate CRF: body temperature, blood chemistry (including Liver Function Tests (LFTs) and Complete Blood Cell Count (CBC)). Study treatment can be started again following recommendation of the dermatologist and investigator. Study treatment must be permanently discontinued thereafter if allergic dermatitis appears again after re-initiation of study treatment. All decisions should be documented in the patient's medical chart.

- Hepatic enzyme elevation – Refer to [Appendix 2](#) for requirements for temporary and permanent discontinuation of study medication.

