- Abnormal hematology evaluation, defined as any of the following, requires temporary discontinuation of study medication and repeat testing within 48 hours (via central or local laboratory) and follow-up until recovery to \leq grade 1 Common Terminology Criteria for Adverse Events (CTCAE). Study treatment must be permanently discontinued thereafter if hematology values are abnormal again (as defined below) after re-initiation of study treatment.
 - Platelets $<50 \times 10^9/L$
 - Absolute neutrophil count $<1.0 \times 10^9/L$
 - Hemoglobin $<80 \text{ g/L}$

If discontinuation of study treatment occurs, the patient should NOT be considered withdrawn from the study. The patient should return to the clinic as soon as possible, after discontinuation of study drug, for a study treatment discontinuation visit as detailed in [Table 6-1](#). The investigator must determine the primary reason for the patient's premature discontinuation of study treatment and record this information in the on the Dosage Administration eCRF.

Patients who discontinue study drug should be treated according to the best standard of care and be encouraged to stay in the study and continue to be followed with an abbreviated schedule of assessments as indicated in [Table 6-2](#).

If the patient cannot or is unwilling to attend any visit(s), the site staff should maintain regular telephone contact with the patient, or with a person pre-designated by the patient. This telephone contact should preferably be done according to the abbreviated study visit schedule.

The investigator must also contact the IRT to register the patient's discontinuation from study treatment.

If study drug discontinuation occurs because treatment code has been broken, please refer to [Section 5.5.9](#).

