6.3 Treatment exposure and compliance

Compliance will be assessed by the investigator and/or study personnel at each visit using pill counts and information provided by the patient. This information should be captured in the source document at each visit. All study treatment dispensed and returned should be recorded in the Drug Accountability Log.

Investigator should also check the electronic patient diaries and remind the patient of the importance of daily completion.

Protocol Deviations should be recorded for patients with an overall study medication compliance of less than 80% or patients with more than 3 full consecutive days of missed doses (more than 6 consecutive doses).

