- its outcome (not recovered/not resolved; recovered/resolved; recovering/resolving; recovered/resolved with sequelae; fatal; or unknown)

All adverse events must be treated appropriately. Treatment may include one or more of the following:

- no action taken (e.g. further observation only)
- investigational treatment interrupted/withdrawn
- concomitant medication or non-drug therapy given
- non-drug therapy given
- patient hospitalized/patient's hospitalization prolonged (see [Section 7.2](#) for definition of SAE)

Once an adverse event is detected, it must be followed until its resolution or until it is judged to be permanent, and assessment must be made at each visit (or more frequently, if necessary) of any changes in severity, the suspected relationship to the study drug, the interventions required to treat it, and the outcome.

Information about common side effects already known about the investigational drug can be found in the Investigator's Brochure (IB). This information will be included in the patient informed consent and should be discussed with the patient during the study as needed. Any

new information regarding the safety profile of the medicinal product that is identified between IB updates will be communicated as appropriate, for example, via an Investigator Notification (IN) or an Aggregate Safety Finding. New information might require an update to the informed consent and has then to be discussed with the patient.

The investigator must also instruct each patient to report any new adverse event (beyond the protocol observation period) that the patient, or the patient's personal physician, believes might reasonably be related to study treatment. This information must be recorded in the investigator's source documents; however, if the AE meets the criteria of an SAE, it must be reported to Novartis.

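### Protocol 5.5.5 bars every study-drug interruption without exception, while 5.6.2 orders two safety holds and foresees restart after both

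*Protocol*

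**What the plan says.** Protocol 5.5.5 is the section headed for permitted dose adjustments and interruptions. Its whole content is that "Investigational or other treatment dose adjustments and/or interruptions are not permitted".

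Protocol 5.6.2 contains a list of adverse events for which study treatment must be interrupted or discontinued. It has three entries:

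- **Skin rash.** "Study treatment should be interrupted if allergic dermatitis is suspected". Afterwards, "Study treatment can be started again following recommendation of the dermatologist and investigator". A second appearance after restart means a permanent stop.
- **Abnormal haematology.** Any of platelets below 50 x 10^9/L, neutrophils below 1.0 x 10^9/L or haemoglobin below 80 g/L "requires temporary discontinuation of study medication and repeat testing within 48 hours", with follow-up until recovery to grade 1 or better. A permanent stop follows only if values are abnormal again "after re-initiation of study treatment".
- **Hepatic enzyme elevation.** The reader is sent to Appendix 2 "for requirements for temporary and permanent discontinuation of study medication".

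Interruption is discretionary elsewhere. Section 7.3 mentions considering it for a confirmed liver laboratory trigger. One row of Table 14-2 (Appendix 2) and two rows of Table 15-1 (Appendix 3) tell the investigator to consider it.

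**The concern.** The section that a site would consult to learn whether drug may be paused says that it may not. A later section orders a pause for two kinds of event. Neither text refers to the other, and both cannot be followed for the same patient.

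The events matter. Protocol 9.5.2.2 names three potential risks of EMA401: allergic dermatitis, raised hepatic enzymes and neutropenia. The two ordered holds cover the first and the last. Read literally, 5.5.5 would keep a patient on drug during just those events. For the remaining risk, 5.6.2 points to a temporary rule in Appendix 2 that is hard to find there.

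**Working it through.** There is no planned figure to reproduce and no arithmetic beyond counting. The check sets the provisions side by side.

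**Step 1: the ban against the orders in 5.6.2.**

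| Event (5.6.2) | Hold | Restart | Fits 5.5.5? |
|---|---|---|---|
| Suspected allergic dermatitis | Ordered | On the advice of dermatologist and investigator | No |
| Abnormal haematology | Ordered | Foreseen; permanent stop on recurrence | No |
| Hepatic enzyme elevation | Referred to Appendix 2 | Referred to Appendix 2 | See step 3 |

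The rash sentence uses a softer verb than the haematology one, but the lead-in to the list is mandatory, so both count as orders. Two of the three categories in 5.6.2 conflict directly with 5.5.5. Since neutrophils are one of the three haematology criteria, two of the three potential risks in 9.5.2.2 have an ordered hold that 5.5.5 bars.

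**Step 2: the discretionary provisions.** Section 7.3, the Table 14-2 row for adverse events suggesting liver toxicity, and the Table 15-1 rows for acute kidney injury and for proteinuria or a raised ratio all let the investigator consider interruption. None is an order. They are out of line with a rule that permits no interruption at all, but the contradiction does not depend on them.

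**Step 3: the hepatic pointer.** Table 14-2 has 11 rows:

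- 5 say to discontinue immediately: potential Hy's Law case; ALT/AST above 8 x ULN; above 3 x ULN with INR above 1.5; above 3 x ULN with symptoms; jaundice.
- 2 say to discontinue if the elevation persists: ALT/AST above 5 to 8 x ULN; isolated bilirubin above 2 x ULN.
- 1 says to consider interruption or discontinuation: adverse event suggesting liver toxicity.
- 3 contain no stop: asymptomatic ALT/AST above 3 to 5 x ULN; isolated ALP above 2 x ULN; bilirubin above 1.5 to 2 x ULN.

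5 + 2 + 1 + 3 = 11. None of the 7 rows that order a stop says whether it is temporary or permanent, and none of the 11 gives a restart criterion. Footnote c defines resolution for monitoring and does not tie it to restarting drug. Redaction does not explain the gap: the actions column is legible, and the blacked-out text is in the follow-up column.

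**The case against.** The best reply is that 5.6.2 is the later, event-specific safety rule, with its own criteria and conditions, and that no sensible site would let one general line override it. That is probably right. A reader might infer from 5.5.5 that patients would be kept on drug through a rash or neutropenia. The documents do not support this, given the explicit orders in 5.6.2. But the reply shows only that sites can work around the error. The general rule remains false.

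Four further inferences are tempting and should not be drawn.

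- **That a hold under 5.6.2 is a protocol breach because of Section 11.1.** That section expects immediate safety action even where it departs from the protocol. It does not classify an action that the protocol itself orders.
- **That directed holds will be logged inconsistently under Section 6.3.** Its deviation wording covers "more than 3 full consecutive days of missed doses" and is silent on directed holds. Silence does not show that sites will diverge, and no hold lengths or patient numbers are given. Section 7.1 already has the action taken with study drug recorded with each adverse event, and 5.6.2 has rash decisions documented in the chart.
- **That an analysis is affected.** SAP 2.4.1 says compliance is not analysed. The discontinuation rules in SAP 2.5.2 concern permanent stops. No set definition in SAP 2.2 turns on an interruption. SAP 5.6 leaves deviation-based exclusions to be added later, but nothing links them to safety holds.
- **That many provisions oppose the ban.** Section 7.1 lists "investigational treatment interrupted/withdrawn" among possible responses to any adverse event. That is a generic list, and the lines that say only to consider interruption are not orders either. The mandatory conflicts number two.

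On the liver, it is fair to say that Appendix 2 is not silent and that 5.6.2 uses the word discontinuation for temporary stops too. The stop rows of Table 14-2 therefore cannot be assumed permanent. What stands is narrower: the table does not say which they are, or when drug may resume.

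**Conclusion.** The contradiction is real and can be read directly from the protocol. Section 5.5.5 is wrong as written for two ordered holds, which cover two of the three named potential risks, and it is out of line with the discretionary interruptions in 7.3 and Appendices 2 and 3. The hepatic point is a minor companion: the pointer in 5.6.2 promises a distinction between temporary and permanent stops that Table 14-2 does not make.

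This is an internal inconsistency in safety instructions and is worth correcting for that reason. It has no claimed effect on dosing in practice, power, alpha, sample size or analysis. The conclusion assumes that the mandatory lead-in in 5.6.2 governs the rash entry. SAP Amendment 1 records early termination with 137 of 400 planned patients randomised, so the point concerns the plan as written, and a correction now would not change care in this trial.

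**What to change.** Reword 5.5.5 to: *Dose adjustments are not permitted. Interruptions are not permitted except for safety reasons as specified in Sections 5.6.2 and 7.3 and Appendices 2 and 3.* If the sponsor also means the 7.1 list to license interruption for any adverse event, 7.1 should be added to that exception.

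Align the hepatic line of 5.6.2 with the appendix, for example: *Refer to Appendix 2 for discontinuation requirements and for when interruption may be considered.* Whether to add a hepatic hold and restart rule instead is a clinical decision for the sponsor.

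The cost is a short wording change in each of two sections. No visit, assessment, threshold or patient is added. Under Section 11.1 the change needs a written amendment with IRB/IEC approval, and health-authority approval where required, across about 100 planned centres. It would therefore best have been made before the protocol was final or together with another amendment.

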5.5.6 Rescue medication

Patients will be allowed to take acetaminophen/paracetamol up to a maximum of 3 g daily (divided into 4 times per day) for unacceptable pain due to any reason during the study.

The patients will be instructed to fill out the electronic pain diary (eDiary) before intake of acetaminophen/paracetamol. Use of acetaminophen/paracetamol must be recorded in the eDiary.

5.5.7 Concomitant medication

The investigator must instruct the patient to notify the study site about any new medications he/she takes after enrolling into the study. All medications including antidiabetic medications, procedures and significant non-drug therapies (including physical therapy and blood transfusions) administered after the patient was enrolled into the study must be recorded in the concomitant medications/significant non-drug therapies eCRF.

Each concomitant drug must be individually assessed against all exclusion criteria/prohibited medication. If in doubt the investigator should contact the Novartis medical monitor before randomizing a patient or allowing a new medication to be started.

1. Patients will be allowed to take **only one** of the following prescribed medications for managing their PDN, provided the dose level has been stable for at least 2 weeks prior to the Screening Visit (Visit 1) and must remain at stable doses throughout the study (PRN (as needed) use is not allowed):
 - Pregabalin
 - Duloxetine
2. In addition to other medications for non-pain related co-morbid conditions, patients will be allowed to take throughout the study the following medications for other concomitant medical conditions. The dose level must be stable at Baseline and must continue at stable doses throughout the study (PRN (as needed) use is not allowed):
 - A benzodiazepine, zolpidem, diphenhydramine or related drugs for insomnia.

- A selective serotonin reuptake inhibitor (SSRI) for depression.
- Oral aspirin (≤ 325 mg/day) for cardio-protection.

